2.0 OBJECTIVES AND PURPOSE

2.1 Primary Objective:

Characterize the pharmacokinetics of vitamin D3 and 25(OH)D3 with a single, high-dose of vitamin D3 in adults with CF.

Compare the pharmacokinetics of vitamin D3 and its metabolites between non-cystic fibrosis controls with low vitamin D levels and adults with cystic fibrosis

2.2 Secondary Objective:

Assess the anti-inflammatory effects of high dose vitamin D therapy in adults with CF.

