3.0 STUDY DESIGN

This is a pilot study to determine the pharmacokinetics-pharmacodynamics of vitamin D3 in CF patients. Clinically stable CF patients with a history of pancreatic insufficiency (n=6) and matching non-CF subjects (n=6) will be recruited in this study. The presence of pancreatic insufficiency will be based on a known CF genotype associated with pancreatic insufficiency. All subjects will be pre-screened for 25(OH)D status to include those with 25(OH)D levels below 30 ng/mL. The subjects will receive a single oral dose of vitamin D3, known as stoss therapy. The dose of stoss therapy will be based on patient's baseline serum 25-hydroxyvitamin D3 level. For CF patients, the dose will be administered with food and pancreatic enzyme supplement to maintain nutritional status. This dose was chosen because previous studies in pediatric CF patients demonstrated that a large single dose of up to 600,000 IU vitamin D3 raised and maintained sufficient 25(OH)D concentrations over 12 weeks without any signs of adverse events (25, 26).

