10.0 CRITERIA FOR EVALUATION AND ENDPOINT DEFINITIONS

Primary Outcome Measure

1. Peak plasma concentrations (C_{max})
2. Time taken to reach the maximum concentration (T_{max})
3. Area under the plasma concentration versus time curve (AUC)

Secondary Outcome Measure

1. Levels of serum inflammatory biomarkers
 - Changes in IL-6, IL-8, TNF- α , IL-1 β , C-reactive protein

11.0 SPECIAL INSTRUCTIONS:

Blood samples will be taken at baseline (0 h) and at 2, 4, 6, 8 hours and 1, 7, 28, 56 and 70 days after intervention. At each defined time points, 5 mL of venous blood will be collected in serum separator tubes (BD Vacutainer) with clot activator (39) to measure serum vitamin D₃ and 25(OH)D₃ concentrations. Samples will be handled with care to minimize sunlight exposure during the time of collection. Samples will be immediately placed on ice and stored in aliquots at -80 °C until analysis. Serum levels of vitamin D₃ and its metabolites will be determined using LC/MS-MS. Levels of inflammatory biomarkers will also be determined at each defined time points.

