13.0 STATISTICAL CONSIDERATIONS

13.1 Pharmacokinetic Analysis

Population pharmacokinetic analysis will be performed using the maximum likelihood estimation via the EM algorithm (MLEM) as implemented in ADAPT 5 (Biomedical Simulations Resource, University of Southern California). Multiple candidate models will be evaluated to identify the model that best describes the observed plasma concentration data for vitamin D3 and 25(OH)D3. The maximum concentration and time to maximum concentration will be determined from the observed data.

Patient demographics, clinical characteristics, and pharmacokinetic parameters will be summarized using descriptive statistics.

Differences in the pharmacokinetic parameters between non-CF controls and CF patients will be determined by non-parametric Wilcoxon-Mann Whitney test.

13.2 Comparison of mean serum and plasma concentrations of inflammatory markers at baseline and 10 weeks post intervention

Mean serum/plasma concentrations of inflammatory biomarkers will be compared between CF and non-CF, as well as within groups. Differences in the mean concentrations of inflammatory markers will be determined by non-parametric Wilcoxon-Mann Whitney test.

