13.3 Pharmacodynamic model of vitamin D3

Time course of inflammatory responses to vitamin D3 treatment will be used to develop the pharmacodynamics model of vitamin D3.

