Appendix I: Study Calendar

Appendix I

	Screening	Day 0	Day 1	Day 7	Day 28	Day 56	Day 70
Informed Consent	X						
Medical History	X						
Medication History	X						
Height, weight	X						
Vital signs ^A	X	X	X	X	X	X	X
Safety labs ^B	X			X			
Pre-screening of 25OHD status	X						
PO drug administration		X					
Blood Pharmacokinetics (PK) ^C		X	X	X	X	X	X
Blood inflammatory biomarkers		X	X	X	X	X	X
Adverse Events		X	X	X	X	X	X

A. Vital signs to include blood pressure, heart rate, temperature, respiratory rate.

B. Safety labs to include comprehensive metabolic panel

C. All subjects will have a pre dose blood PK levels, 2, 4, 6, 8 hours and 1, 7, 28, 56, 70 days post dose of cholecalciferol. A 5mL serum separator tube will be used to collect the blood sample.

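### The only biomarker test (13.2) is headed baseline and week 10, leaving days 1–56 to a model with no stated comparison, and it uses an independent-samples test within groups

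*Combined protocol and SAP*

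**What the plan says.** The secondary objective in 2.2 is: "Assess the anti-inflammatory effects of high dose vitamin D therapy in adults with CF". Section 10.0 lists the outcome as "Levels of serum inflammatory biomarkers", meaning changes in five markers (IL-6, IL-8, TNF-α, IL-1β, C-reactive protein), and gives no time point.

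Section 11.0 sets ten sampling times ("Blood samples will be taken at baseline (0 h) and at 2, 4, 6, 8 hours and 1, 7, 28, 56 and 70 days after" the intervention) and adds: "Levels of inflammatory biomarkers will also be determined at each defined time points". The row "Blood inflammatory biomarkers" in Appendix I marks six visit days: 0, 1, 7, 28, 56 and 70.

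Section 13.2 carries the heading "Comparison of mean serum and plasma concentrations of inflammatory markers at baseline and 10 weeks post intervention". Its body gives no times. It says mean concentrations will be compared between CF and non-CF and within groups, and names one test for both, Wilcoxon-Mann-Whitney. Section 13.3 is a single sentence: "Time course of inflammatory responses to vitamin D3 treatment will be used to develop the pharmacodynamics model" of vitamin D3. Section 3.0 sets the size at six CF patients and six matching non-CF subjects.

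**The concern.** There are two separate problems.

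- **Times.** As headed, the only hypothesis test for the secondary objective rests on one post-dose value per subject, the last one, ten weeks after a single dose. The values from days 1–56 go to a model for which no markers, effect parameter or contrast are named. The plan therefore does not say how those values will bear on whether inflammation changed. If an effect had faded by day 70, the test would miss it although the trial had measured it.
- **Test.** The within-group comparison sets each subject's later value against the same subject's baseline. The Wilcoxon-Mann-Whitney test treats the two sets as unrelated people. Stable differences between subjects then count as noise, and the gain from using each subject as their own control is lost.

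**Working it through.** The documents give no SD, correlation, effect size, alpha or power for the markers, so there is no stated figure to reproduce. Everything below except the counts and n = 6 is assumed for illustration: two-sided 0.05, one marker on its analysis scale, and effects in units of the within-subject SD.

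**1. Share of the schedule tested.** Two of six visit days (33%) by Appendix I, or two of ten samples (20%) if section 11.0 is read literally.

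**2. Precision of the change from baseline.** In units of the within-subject variance, with independent errors:

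- Day 70 minus baseline: 1 + 1 = 2.
- Mean of days 7, 28, 56 and 70 minus baseline: 1 + 1/4 = 1.25.
- SE ratio: √(1.25/2) = 0.79.

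If errors instead have correlation exp(−gap/14 days), the variances are 1.987 and 0.969, and the ratio is 0.70. The same ratios apply to the between-group difference in change, because each group's variance shrinks by the same factor.

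**3. Power of the signed-rank test, n = 6.** Its smallest exact two-sided p is 2/2⁶ = 0.03125, reached only when all six changes have the same sign. No other outcome gives p ≤ 0.05. With normal errors, power is therefore Φ(z)⁶ + [1 − Φ(z)]⁶, where z is the mean change divided by its SD.

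Example, sustained shift of 1.5, independent errors:

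- Day 70: z = 1.5/√2 = 1.061, Φ = 0.856, power 0.39.
- Average: z = 1.5/√1.25 = 1.342, Φ = 0.910, power 0.57.

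| Effect at days 7, 28, 56, 70 | Mean effect | Day 70 alone | Average, independent / 14-day correlation |
|---|---|---|---|
| Sustained: 1.5, 1.5, 1.5, 1.5 | 1.5 | 39% | 57% / 67% |
| Fading: 1.5, 1.5, 0.75, 0 | 0.9375 | 3% | 26% / 33% |
| Absent at day 7: 0, 1.5, 1.5, 1.5 | 1.125 | 39% | 36% / 44% |
| Gradual onset: 0, 0.75, 1.5, 1.5 | 0.9375 | 39% | 26% / 33% |
| Day 70 only: 0, 0, 0, 1.5 | 0.375 | 39% | 7% / 8% |

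A simulation with 200,000 runs agrees to within rounding. If subjects also differ in their true response (SD of 1 within-subject SD), a sustained mean shift of 1.5 gives 28% at day 70 and 35–40% for the average.

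**4. Wilcoxon-Mann-Whitney on paired data.** Assume a between-subject SD of twice the within-subject SD. The paired difference has variance 2 × 1 = 2, but the test in effect works against 2 × (4 + 1) = 10. By simulation (200,000 runs, exact critical value), its false-positive rate is about 0.2% and its power for a 1.5 shift is 8%. The signed-rank test has 3.1% and 39% on the same data.

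**5. Multiplicity.** Five markers under Bonferroni need p ≤ 0.05/5 = 0.01. The within-group floor of 0.031 cannot meet that with either summary. The 6-versus-6 Mann-Whitney floor is 2/924 = 0.0022.

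**The case against.** A reader might infer that the plan throws away most of the biomarker data. It does not. Section 13.3 assigns the time course to the pharmacodynamic model, and section 3.0 presents the trial as a pharmacokinetic-pharmacodynamic pilot, so that model is central. A fixed two-point test beside a longitudinal model is a defensible design. What remains is that 13.3 states no comparison. That silence does not prove none is intended.

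The two-point limit also appears only in the heading of 13.2. This stands as a caveat, but no other passage names a different time for the test.

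A second tempting inference is that the average should replace day 70. The table does not support that. The gain needs an effect that is present early and lasts, and a gradual onset is enough to reverse it. Section 1.0 reports wide variation in response to vitamin D in people without CF, and such variation shrinks the gain. Section 3.0 says earlier data showed 25(OH)D maintained over 12 weeks, so a week-10 endpoint fits the protocol's own rationale. That statement concerns 25(OH)D and not the inflammatory markers, so it does not rule out a fading effect.

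Finally, this is a secondary objective in a pilot with no stated alpha or power. That limits how much the point matters, but it does not make an independent-samples test suitable for paired data.

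**Conclusion.** The point holds in two parts.

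- The test mismatch does not depend on the shape of the effect. Its cost depends on how much subjects differ: 8% against 39% power if the between-subject SD is twice the within-subject SD.
- The time-point limit is a gap in what is tested. Adding the average helps with a sustained effect (39% to 57–67%) or a fading one (3% to 26–33%) and hurts with a gradual onset (39% to 26–33%) or an effect only at day 70 (to 7–8%). This supports reporting both summaries and does not support swapping one for the other.

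All power figures rest on assumed effects and correlations, six patients with complete data, and one marker without multiplicity adjustment. No version of this analysis can attribute a change to vitamin D, because every subject is dosed and there is no untreated arm.

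**What to change.** In 13.2:

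1. Name the paired Wilcoxon signed-rank test for within-group comparisons, and apply Mann-Whitney to each subject's change from baseline between groups.
2. State the times in the body text. Keep day 70 and add, pre-specified, each subject's mean (or time-weighted mean) log change from baseline over days 7–70. Report both for every marker.
3. Label the results exploratory and describe them as change after dosing.

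In 13.3, or by cross-reference from it, say how the modelled time course will inform the secondary objective.

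This changes wording only and needs no extra visits, samples or assays. The cost is one more comparison per marker, and an average that dilutes a late effect. Reporting day 70 beside it keeps such an effect visible.

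### Section 13.2 names only an independent-samples test (Wilcoxon-Mann-Whitney) for the within-group baseline versus week-10 biomarker comparison, although both values come from the same subjects

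*Combined protocol and SAP*

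**What the plan says.** All references are to the combined protocol and SAP.

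- **Section 13.2, heading:** the marker concentrations are to be compared "at baseline and 10 weeks post intervention".
- **Section 13.2, text:** "Mean serum/plasma concentrations of inflammatory biomarkers will be compared between CF and non-CF, as well as within groups". The next sentence gives the method for all of this: "Differences in the mean concentrations of inflammatory markers will be determined by non-parametric Wilcoxon-Mann Whitney test".
- **Section 3.0:** the sample is "Clinically stable CF patients with a history of pancreatic insufficiency (n=6) and matching non-CF subjects (n=6"). Both groups are dosed: "The subjects will receive a single oral dose of vitamin D3".
- **Section 11.0 and Appendix I:** markers are measured at every sampling time. The calendar row "Blood inflammatory biomarkers" is ticked at each visit from Day 0 to Day 70, so each subject supplies both values.
- **Section 10.0:** the secondary outcome is marker levels, with the sub-item beginning "Changes in IL-6, IL-8" and listing five markers in all.
- **Section 2.2:** the secondary objective is the anti-inflammatory effect in adults with CF.
- **Section 13.3:** "Time course of inflammatory responses to vitamin D3 treatment will be used to develop the pharmacodynamics model of vitamin D3". No test, estimate of change or contrast is stated there.

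**The concern.** The Mann-Whitney null distribution assumes that the two sets of values are independent. Baseline and week-10 values from one subject are not, because a subject with a high marker at baseline will usually still be high ten weeks later. Applied to such data, the named test counts the spread between subjects as noise, although subtracting each subject's own baseline would remove much of it.

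Objective 2.2 concerns adults with CF, so the within-CF comparison answers it most directly. That is where the named test does not fit the data. The risk is that a fall seen in every CF subject is reported as no difference. The reported p-value would also have a true size that depends on an unknown correlation.

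**Working it through.** **What there is to reproduce.** The document gives no significance level, SD, effect size, power or within-subject correlation for the markers. The only input taken from it is n = 6 per group. Everything else below is an assumption: two-sided 0.05, normal values with SD 1 at both times, correlation ρ from 0 to 0.7, and falls of 0 to 1.5 SD. There were 200,000 simulated data sets per setting, using exact critical values.

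**Why pairing matters.** For one subject, Var(week 10 − baseline) = 2(1 − ρ)SD². Treating the values as independent amounts to using 2SD². At ρ = 0.5 the true figure is 2 × 0.5 = 1, half of 2. At ρ = 0.7 it is 2 × 0.3 = 0.6, or 30% of it.

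**Exact limits of each test.**
- Mann-Whitney, 6 v 6: there are C(12,6) = 924 arrangements, so the minimum two-sided p is 2/924 = 0.002. The largest attainable level not above 0.05 is 0.041 (U ≤ 5).
- Signed-rank, six pairs: there are 2⁶ = 64 sign patterns, so the minimum p is 2/64 = 0.031, reached only if all six subjects move the same way. The matching interval has 1 − 2/64 = 96.9% confidence and is the range of the six changes.
- Signed-rank, five pairs: the minimum p is 2/32 = 0.0625, and the highest interval level is 93.75%.

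**Within-group rejection rates, n = 6 (Mann-Whitney / signed-rank).**

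| ρ | no change | fall 0.5 SD | fall 1 SD | fall 1.5 SD |
|---|---|---|---|---|
| 0 | 4.1% / 3.1% | 10% / 7% | 30% / 19% | 58% / 39% |
| 0.3 | 2.0% / 3.1% | 8% / 9% | 28% / 26% | 60% / 52% |
| 0.5 | 1.0% / 3.1% | 6% / 11% | 27% / 35% | 62% / 66% |
| 0.7 | 0.4% / 3.1% | 4% / 17% | 26% / 54% | 64% / 85% |

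Repeat runs differ by up to about one percentage point. The paired test overtakes at ρ of about 0.25, 0.35 and 0.45 for falls of 0.5, 1 and 1.5 SD. Below that the named test has the greater power.

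**One pair lost (five pairs).** Signed-rank power at 0.05 is 0% whatever the effect. Mann-Whitney has 16% to 18% at a 1 SD fall (ρ 0.3 to 0.7) and about 43% at 1.5 SD.

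**Worked example (invented values, a favourable case for pairing).** Baselines are 1, 2, 4, 8, 16, 32 and every subject falls 30%, giving 0.7, 1.4, 2.8, 5.6, 11.2, 22.4. The week-10 values exceed 0, 1, 2, 3, 4 and 5 of the baselines in turn, so U = 15 and exact Mann-Whitney p = 0.70. All six changes are negative, so signed-rank p = 0.031. The Hodges-Lehmann ratio on the log scale is 0.70.

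**The case against.** The strongest reply is that the mismatch is harmless or even helpful. Mann-Whitney stays at or below 4.1% type I error at every correlation of zero or above, so it cannot produce false anti-inflammatory claims beyond the nominal level. At low correlation it has more power than signed-rank, and it survives a dropout that leaves signed-rank unable to reach 0.05. The endpoint is secondary, the study is a pilot, and the paired data are collected anyway. For a 0.5 SD fall neither test exceeds about 17% power at correlations up to 0.7.

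Most of this stands, and it limits the severity. It does not remove the point, because the plan names a test whose reference distribution does not hold for the data. It might also be said that the signed-rank test was meant. However, the same two-sample name is used in Section 13.1 for CF versus non-CF, so the text does not show that.

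Three stronger readings are tempting and are not supported:

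- **That the analysis would yield spurious positives.** With positive correlation it does the opposite.
- **That power is certainly lost.** The document gives no correlation, and below about 0.25 to 0.45 the loss goes the other way.
- **That the plan must compare change between groups because Section 10.0 lists changes.** That item sits under marker levels, and within-group change plus between-group levels is a defensible reading. A claim of different response in CF and non-CF would go beyond objective 2.2. Any distortion from comparing levels needs an assumed baseline gap. With no gap and correlation below about 0.5, testing change has less power than testing week-10 levels. Section 3.0 also does not say whether matching is individual, which would bear on any between-group test.

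**Conclusion.** The point holds for the within-group comparison only. Section 13.2 plans it, names an independent-samples test for it, and no other section supplies a paired analysis. This follows from the text alone and needs no assumption.

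The consequence is conservatism and a possible missed effect. At a 1 SD fall and correlation 0.7 the named test would detect it in about 26% of trials, against 54% for the paired test. At correlation 0.3 the two are close (28% against 26%). These figures rest on normal data, equal SDs, a 0.05 level and six complete pairs, and apart from the group size none of this is in the document.

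Severity is minor to moderate: a secondary outcome of a pilot, correctable before analysis, with data collection and the primary pharmacokinetic endpoints unaffected.

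**What to change.** Amend Section 13.2 as follows.

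1. For the within-group comparison, analyse each subject's baseline to week-10 change on one scale fixed in advance, for example the log scale, which gives a ratio. The scale must be named because signed-rank and Hodges-Lehmann results can change with it, whereas Mann-Whitney does not change under a log transform.
2. Lead with the Hodges-Lehmann estimate and its exact confidence interval, and give the Wilcoxon signed-rank test in support.
3. Keep Mann-Whitney for CF versus non-CF.
4. State the limits:
   - Power is below Mann-Whitney's at low within-subject correlation (below about 0.25 to 0.45 under the assumptions above).
   - The minimum two-sided p is 0.031 with six pairs, so a Bonferroni threshold of 0.05/5 = 0.01 for the five markers cannot be reached.
   - The minimum p is 0.0625 if one pair is lost, or if one change is zero and is dropped in the usual way. That leaves estimation only.

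Optional side remark: if a between-group statement about response is wanted, say how change will be compared and whether the matching is individual.

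The cost is a few sentences in Section 13.2, with the same subjects, samples and assays. The statistical cost is the set of limits in item 4.

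### Objective 2.2 is about adults with CF, but section 13.2 spreads it over at least 15 unranked, unpaired marker tests with no lead contrast and no exploratory label

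*Combined protocol and SAP*

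**What the plan says.** Section 2.2 gives the secondary objective: "Assess the anti-inflammatory effects of high dose vitamin D therapy in adults with CF". Section 10.0 lists the outcome as "Changes in IL-6, IL-8, TNF- α , IL-1 β , C-reactive protein", five markers in no order of importance.

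The heading of 13.2 confines the tests to two time points: "Comparison of mean serum and plasma concentrations of inflammatory markers at baseline and 10 weeks post intervention". Under it stand "Mean serum/plasma concentrations of inflammatory biomarkers will be compared between CF and non-CF, as well as within groups" and "Differences in the mean concentrations of inflammatory markers will be determined by non-parametric Wilcoxon-Mann Whitney test".

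Section 3.0 sets the size and status of the study: "Clinically stable CF patients with a history of pancreatic insufficiency (n=6) and matching non-CF subjects (n=6) will be recruited in this study" and "This is a pilot study to determine the pharmacokinetics-pharmacodynamics of vitamin D3 in CF patients". Section 11.0 measures the markers at every sampling time ("Levels of inflammatory biomarkers will also be determined at each defined time points"), but 13.3 assigns that time course to a pharmacodynamic model, not to tests.

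The plan gives no significance level, lead marker, lead contrast, multiplicity rule or criterion for declaring an anti-inflammatory effect. Nothing in 13.2 calls these comparisons exploratory.

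**The concern.** The contrasts in 13.2 answer different questions.

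- The change within CF is the one that bears on 2.2.
- The change within non-CF concerns people outside the objective.
- A CF v non-CF difference in levels at week 10 cannot be put down to treatment. Both groups are dosed, and CF patients may be more inflamed to begin with.
- A between-group comparison of change asks whether the response differs, not whether there is one.

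With no contrast in the lead, a small p-value on any of them could be reported under the secondary objective, and two contrasts could point in opposite directions with no rule for which counts.

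The choice of test adds to this. The within-CF comparison has each patient at two times, but the named test treats the two sets of values as independent samples.

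**Working it through.** **Inputs.** Five markers (10.0). Six CF and six non-CF subjects (3.0). Baseline and week 10 only (heading of 13.2). Wilcoxon-Mann-Whitney throughout (13.2). Assumptions, because the documents are silent: two-sided 0.05 per test; correlation between markers 0 to 0.8; correlation between baseline and week 10 in the same subject 0 to 0.8. The plan has no error rate or power figure of its own to reproduce.

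**Count.** 5 markers x 3 contrasts (within CF, within non-CF, CF v non-CF at week 10) = 15. A fourth contrast, such as CF v non-CF at baseline or on change, makes 20.

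**Exact size of one test.**
- Mann-Whitney, 6 v 6: there are 924 arrangements, and the two-sided rejection region at 0.05 holds 38. Size 38/924 = 0.041; smallest p 2/924 = 0.002.
- Signed-rank, n = 6: only six changes in the same direction reach 0.05. Size and smallest p are both 2/2^6 = 0.031.

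**Five tests with independent markers.**
- Signed-rank: 1 - (1 - 0.03125)^5 = 0.147. Falls only: 1 - (1 - 0.015625)^5 = 0.076.
- Mann-Whitney on independent samples: 1 - (1 - 0.0411)^5 = 0.189.

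**Correlated data.** In 40,000 simulated null trials per setting (normal data, no change, groups alike), the chance of at least one p below 0.05 was as follows. Each range runs over between-marker correlations 0 to 0.8.

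| Tests counted | Visit correlation 0 | 0.5 | 0.8 |
|---|---|---|---|
| 15, as written | 0.29-0.44 | 0.18-0.26 | 0.13-0.20 |
| 15, paired within groups | 0.27-0.39 | 0.29-0.40 | 0.28-0.41 |
| 5 within CF, as written | 0.12-0.19 | 0.04-0.05 | below 0.01 |
| 5 within CF, paired | 0.10-0.15 | 0.11-0.15 | 0.10-0.15 |
| 5 within CF, paired, falls only | 0.05-0.08 | 0.05-0.08 | 0.05-0.08 |

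**Power for one marker within CF**, for a true fall of 0.8 SD of the marker level. The change has SD sqrt(2(1 - r)) in units of the level SD, where r is the visit correlation. The paired test rejects for a fall with probability Phi(0.8/SD of change)^6.
- r = 0.5: SD of change 1, so 0.788^6 = 0.24. The unpaired test, simulated, gives 0.16.
- r = 0.8: SD of change 0.632, so 0.897^6 = 0.52. Unpaired: 0.14.
- r = 0: SD of change 1.414, so 0.13. Unpaired: 0.21. Pairing loses power only when the visits are nearly uncorrelated.

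**Correction over five markers.** Paired: 5 x 0.03125 = 0.156, so Bonferroni or Holm can never reach 0.05. Unpaired: 5 x 2/924 = 0.011, so a correction is possible with the test as written.

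**The case against.** The strongest reply is that this is a 12-subject pilot, that the markers serve one secondary objective, and that 13.2 already fixes two time points and attaches no decision rule to any p-value. Formal multiplicity control would be out of proportion. That stands, and it is why the request is for a lead contrast and a label, not for a split significance level. It does not remove the gap: calling the study a pilot does not make these tests descriptive when 13.2 says that differences are to be determined by a hypothesis test.

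A reader might infer three stronger things that the documents do not support.

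- *That an anti-inflammatory effect has a 1 in 5 to 1 in 4 chance of false support.* That is about what five independent two-sided tests at 0.05 give (1 - 0.95^5 = 0.226). On the contrast that addresses 2.2, the paired rate is 0.10 to 0.15. A rise in a marker cannot support the objective, and counting only falls gives 0.05 to 0.08. Larger figures rely on contrasts that do not answer 2.2, or on baseline and week 10 being uncorrelated in the same person.
- *That the plan as written cannot be rescued by a multiplicity correction.* The 0.156 floor belongs to the paired test, not to the test the plan names.
- *That every sampling time multiplies the tests.* The 13.2 heading and 13.3 rule this out.

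It is also fair to object that resting the objective on one marker is a debatable choice in so small a study. The fix therefore leaves that choice open.

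**Conclusion.** The gap is real, but it concerns which contrast answers the objective and which test suits it more than a large error rate on the relevant question. The as-written range of 0.13 to 0.44 for 15 tests applies only if any significant result could be taken as support. It also assumes a global null in which CF and non-CF subjects are equally inflamed; if they are not, a significant week-10 difference is a disease difference, not a false positive for treatment. On the within-CF change alone, the unpaired test is conservative when visits correlate at 0.5 or more, so the cost there is lost power rather than false claims. All rates rest on the assumed two-sided 0.05, normal data and the correlation ranges shown. Even the within-CF change remains an uncontrolled before-after comparison, since no group goes untreated. Severity is minor to moderate.

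**What to change.** In 13.2, replace the two sentences on the comparisons with text to this effect: *Objective 2.2 is assessed by the change from baseline to week 10 within the CF group, using an exact paired Wilcoxon signed-rank test. All other contrasts (within non-CF, and CF v non-CF) are exploratory and are reported as estimates with intervals; between-group comparisons are made on change from baseline.*

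Then add one of two sentences:

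- The sponsor names one lead marker, marked in 10.0, before the markers are assayed. Its test has size 0.031. Section 11.0 stores samples at -80 °C until analysis but does not say when assays are run, so the sponsor should confirm that the choice comes first.
- All five within-CF results are reported together as exploratory, with estimates and intervals, and no effect is claimed from a single marker.

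The change needs a few sentences and no new subjects, samples or assays. It has three costs. A result on a non-lead marker or contrast can no longer be presented as meeting the objective. A single lead marker has low power (0.24 in the r = 0.5 case above). And if one CF patient lacks a week-10 value, the smallest paired p is 2/2^5 = 0.0625, so the test cannot reach 0.05; that favours the second option if dropout is likely.

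### Section 13.2 compares mean biomarker concentrations with a rank test that does not test means, and names no estimate that matches the test

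*Combined protocol and SAP*

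**What the plan says.** Section 10.0 gives one secondary outcome, "Levels of serum inflammatory biomarkers", detailed as "Changes in IL-6, IL-8, TNF- α , IL-1 β , C-reactive protein". Section 13.2 sets out its analysis. The heading concerns mean concentrations of "inflammatory markers at baseline and 10 weeks post intervention". The text continues: "Mean serum/plasma concentrations of inflammatory biomarkers will be compared between CF and non-CF, as well as within groups", and then: "Differences in the mean concentrations of inflammatory markers will be determined by non-parametric Wilcoxon-Mann Whitney test".

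So the heading and both sentences name the mean, and the only method named is a rank test for independent samples. It is applied to CF v non-CF and also to the within-group comparison.

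No section names a median, a shift estimate, a log scale or a confidence interval for the biomarkers, or assumes equal shapes. Section 13.1 promises descriptive statistics, but for other items: "Patient demographics, clinical characteristics, and pharmacokinetic parameters will be summarized using descriptive statistics". Section 3.0 fixes the size: "Clinically stable CF patients with a history of pancreatic insufficiency (n=6) and matching non-CF subjects (n=6) will be recruited in this study". No significance level or sidedness is stated.

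**The concern.** The quantity named and the test named do not belong together. The rank test asks whether a value from one group tends to exceed a value from the other. It becomes a test of means only under further assumptions, chiefly that the two distributions differ by a shift alone. That is doubtful here: Section 1.0 describes CF as marked by chronic infection and inflammation, and the comparators do not have CF, so spread may differ as well as level.

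A report following Section 13.2 would print a mean difference beside a p-value that does not test it. With six subjects per group and skewed markers, one high value can carry the mean yet counts as a single rank.

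The same sentence also covers baseline v 10 weeks. Those are repeat measurements on the same people, and the independent-samples test does not apply to them.

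**Working it through.** **Inputs.** Group sizes 6 and 6 (Section 3.0); test and quantity (Section 13.2). The documents give no level, variance or effect size, so there is no figure of the plan's own to reproduce. Two-sided 0.05, the log-normal shape and all CVs below are assumptions. The simulations concern concentrations at one time point, not changes. CV converts to log-SD by √ln(1+CV²): 50%, 100% and 200% give 0.47, 0.83 and 1.27.

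**1. Is it a test of means?** A log-normal mean is exp(μ+σ²/2). If two groups have equal means, their medians are in the ratio exp(−(σ₁²−σ₂²)/2).

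| Log-SDs | Ratio of medians at equal means | Rejection at two-sided 0.05 |
|---|---|---|
| Equal (0.5 or 1.0) | 1 | about 4% |
| 1.0 v 0.5 | exp(−0.375) = 0.69 | about 10% |
| 1.5 v 0.5 | exp(−1.0) = 0.37 | about 24% |

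The excess is a response to a difference that the mean does not show. The last row is a strong contrast: CV = √(exp(σ²)−1) gives about 291% v 53%.

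**2. How far does one subject carry the mean?** Equal shares would be 1/6 = 17%. At CV 100-200% the largest of six values supplies a median 36-45% of the group total.

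**3. Can the mean difference and the ranks differ in sign?** Yes. Take A = 1, 2, 3, 4, 5, 60 and B = 6, 7, 8, 9, 10, 11.
- Means are 75/6 = 12.5 and 51/6 = 8.5, a difference of +4.0. Medians are 3.5 and 8.5.
- A exceeds B in U = 6 of 36 pairs. Exact two-sided p = 2×30/924 = 0.065.
- The Hodges-Lehmann shift (median of the 36 differences A−B) is −5.0. Its exact interval runs from the 6th smallest to the 6th largest difference, −8 to 49, with coverage 1−2×19/924 = 95.9%.

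Counting strictly opposite signs in simulation:

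| CV | True ratio 1 | True ratio 1.5 |
|---|---|---|
| 50% | 10% | 3% |
| 100% | 14% | 10% |
| 200% | 18% | 16% |

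**4. Can this accompany a significant result?** Two-sided p≤0.05 needs U≤5 (p = 2×19/924 = 0.041). Suppose the i-th ordered A value exceeds the i-th ordered B value. Then the top 7−i values of A exceed the lowest i values of B, so U≥i(7−i)≥6. Hence at U≤5 every ordered A value lies below its B counterpart, and so does the mean. This holds for any untied values, whatever their distribution. After dropout the smallest exact p with opposite signs is 0.082 (5 v 6), 0.114 (4 v 6) or 0.151 (5 v 5).

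**5. Within groups.** Normal data, six subjects, rejection rates for Wilcoxon-Mann-Whitney v signed-rank, by assumed within-subject correlation:

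| Correlation | No change | 1 SD change |
|---|---|---|
| 0 | 4.2% v 3.1% | 30% v 19% |
| 0.3 | 2.1% v 3.2% | 28% v 26% |
| 0.5 | 1.1% v 3.2% | 27% v 35% |
| 0.7 | 0.4% v 3.0% | 26% v 54% |

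**The case against.** The best defence is that a rank test is a sensible choice for skewed markers at this size, that the word mean is loose drafting, and that nobody would be misled. The first part stands, and is a reason to keep the test. The second is weakened by the repetition of the word in the heading and both sentences, with no other estimate named anywhere.

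A reader might infer that Section 13.2 could yield a significant p-value contradicting the direction of the mean difference. The documents do not support that. A two-sided p-value has no direction, and at 6 v 6 without ties the conflict needs p of at least 0.065; 12 simulated settings of 60,000 trials (720,000 in all) gave none at p≤0.05. Exceptions need a one-sided 0.05 test (U = 6 gives 0.032), a two-sided 0.10 level, or ties. With ties it is possible: A = 0, 0, 0, 0, 0, 60 against B = 1, 1, 1, 2, 3, 4 has means of 10 and 2 and exact p = 0.048. The plan mentions no one-sided test, 0.10 level or detection limit.

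A reader might also take the 10-18% sign disagreement at CV 100-200% as the chance of a misleading conclusion. It is mostly noise around zero. Among those trials the median exact p is 0.70-0.82 and about 95-97% have p>0.3; opposite signs with p≤0.10 occur in 0.05-0.14% of all trials. Geometric means also oppose the ranks in about 6% of trials with no true difference.

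Finally, the Hodges-Lehmann interval has its exact coverage for a shift only if shapes are equal. True, but the estimate remains the median of the 36 pairwise differences. Without ties it agrees in sign with the ranks by construction, because if fewer than 18 differences are positive their median is negative.

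**Conclusion.** The mismatch is real and is cured nowhere else in the documents. Its consequence is that the p-value does not test the reported mean difference. How much that matters depends on how far the group shapes differ, which is unknown: under the assumed log-normal cases, rejection at equal means runs from about 4% (equal shapes) to 24%. The reported mean would also often be carried by one subject. Sign conflict is confined almost entirely to clearly non-significant results.

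The within-group use of an independent-samples test is an error of design type. It costs power at within-subject correlations of 0.5 and 0.7, and not at zero or 0.3.

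Section 3.0 calls the work a pilot ("This is a pilot study to determine the pharmacokinetics-pharmacodynamics of vitamin D3 in CF patients"), and the endpoint is secondary. This is a minor correction.

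**What to change.** Rewrite Section 13.2, including its heading, along these lines:

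- **CF v non-CF:** summarise biomarker concentrations by medians. Compare groups with the exact Wilcoxon-Mann-Whitney test and report the Hodges-Lehmann shift with its exact 95% confidence interval.
- **Baseline v 10 weeks within each group:** use the Wilcoxon signed-rank test on the paired differences, with the paired Hodges-Lehmann estimate and its exact interval.

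**Cost.** Wording only; no new subjects, samples or assays. The intervals will be wide. With six pairs the signed-rank test reaches two-sided 0.05 only if all six differences have the same sign (p = 2/64 = 0.031), and the exact interval is simply the range of the six differences (96.9% coverage). With five complete pairs the smallest p is 2/32 = 0.0625, so no exact 95% interval exists. The plan should say that the 93.75% interval will then be given.

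Analysing log concentrations and reporting geometric mean ratios is a possible alternative. It would change the method rather than the wording, add a distributional assumption at n=6 and need a rule for values below a detection limit. It is not required to settle this point.
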